## **IRB Summary**

- 1. Title:** Utilizing Transcranial Direct Current Stimulation and Gaze Training to Enhance Laparoscopic Technical Skills Training

### **2. Purpose of the Study**

To test the influences of transcranial direct current stimulation (tDCS) and gaze training (GT) on the acquisition of laparoscopic surgical skills. For this purpose, we will compare variants of tDCS and GT in experiments 1 and 2, respectively, and then compare the optimal variants from each of these in experiment 3 in a crossed design with a follow up test of retention. These questions will be evaluated using the validated Fundamentals of Laparoscopic Surgery (FLS) modules 1 and 5, with the overall goal of developing a surgical training curriculum that achieves expert level skill in an expedited timeframe. This research provides a novel approach to general surgery training that has the potential to reduce the amount of time and repetitions required to achieve expert laparoscopic skills.

### **3. Background & Significance:**

Developing expert performance requires assessment of the thought processes underlying performance and continued refinement of skills in order to obtain automaticity and intuition. Therefore, developing expert surgical skill is a process likely to take longer than the length of residency, thereby diminishing the quality of care delivered to patients.

The proposed study will implement novel neuroscience techniques of transcranial direct current stimulation and gaze training to determine if they have the capacity to accelerate technical surgical skill learning in order to achieve competency and expertise in an earlier timeframe. tDCS is a non-invasive brain stimulation technique that delivers constant, low current stimulation via electrodes placed on the scalp to modify cortical excitability in an area of interest. When applied to the motor cortex, promising data indicates that tDCS-induced changes lead to expedited recovery in stroke patients as well as enhanced learning in healthy individuals.

Studies of skill performance have demonstrated that eye movement patterns can be optimized to improve subsequent motor movements. Therefore, gaze training encourages novices to adopt the more efficient gaze patterns of experts while performing a specific task such as laparoscopic surgery. These techniques have never been applied in the training of surgical residents making this project an innovative approach to enhance skill development.

#### 4.Design & Procedures

##### **Experiment 1:** Determine if tDCS can accelerate the learning of laparoscopic skills.

In this experiment, we will compare behavioral learning curves from FLS modules 1 in three cohorts who undergo either active tDCS to the bilateral motor cortex (bilateral configuration), active tDCS to the supplementary motor cortex (SMA configuration), or sham tDCS (half in each configuration). This will be tested in groups of 20 participants who train on FLS module 1 for 40-minutes in 3 sessions that occur within 1-3 weeks. We hypothesize that both active bilateral and SMA tDCS will lead to faster skill acquisition as measured by trials required to gain proficient completion scores (calculated as time plus errors), relative to sham.

We hypothesize that both bilateral and vertex tDCS will lead to faster skill acquisition, with bilateral greater than vertex as measured by trials required to gain proficient module completion scores, relative to the group of participants who practice without active tDCS.

##### **Experiment 2:** Determine if gaze training can accelerate the learning of laparoscopic skills.

In this experiment we will first establish expert gaze patterns in the Fundamentals of Laparoscopic Surgery modules 1 and 5 by testing a total of 9 participants, including attending surgeons, senior residents, and novices trained to proficiency. We will then compare behavioral learning curves from non-expert participants without gaze training against those trained using both explicit (by reviewing the expert gaze pattern) and implicit gaze (by using a visual mask during the training, leading the participant to follow the expert gaze) derived from the expert gaze patterns. This will be tested in 3 groups of 20 participants, who train for 40-minutes in each of 6 sessions that occur within 3 weeks.

We hypothesize that both explicit and implicit gaze training will lead to faster skill acquisition with implicit greater than explicit. These training sessions will be measured by trials required to gain proficient module completion scores relative to the group of participants who practice without any gaze training.

##### **Experiment 3:** Compare tDCS and gaze training in a crossed design to evaluate learning and retention.

In this experiment, we will utilize the most effective active tDCS condition from experiment 1 and the most effective Gaze Training condition from experiment 2 in a crossed design to evaluate learning and retention. In this crossed design, four groups of 20 participants that receive either: active tDCS and gaze training, active tDCS with no gaze training, gaze training with sham tDCS, or just sham tDCS. In each case,

participants will partake in 3-6 sessions of 40-minutes over 1-3 weeks, training on FLS modules 1 and 5, and will also participate in a follow-up FLS assessment 4 to 6 weeks after the completion of training to evaluate the retention of trained skills. We hypothesize that applying tDCS and gaze training will result in additive improvement on learning curves, and will lead to greater retention of trained skills at the follow up assessment, compared to either condition alone or to the sham group.

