## **6. Subject Recruitment and Compensation**

We propose to enroll 249 healthy subjects consisting of Duke medical students, undergrads, surgical residents, and surgical attendings. We anticipate that 40 of the recruited participants will not complete the protocol, with 209 completing the full study. A sample size of 249 was carefully selected. This study includes three separate aims requiring new subjects for each due to the improvement in technical skill from repetition alone. Therefore, the same subjects cannot be utilized in the tDCS portion of the study as well as the gaze training or cross design study.

Prior tDCS studies have enrolled less than 20 subjects per group. For example, Reis et al 2009, which we are using as a model design, used 12 participants per group. Typical gaze training studies within surgery have had very small enrollment numbers of 5-10. Putting this together, we aimed for a cohort of 20 subjects for each intervention. The tDCS portion of the study evaluating bilateral stimulation, SMA stimulation, versus sham will require a total of 60 subjects with 20 in each study arm. As for gaze training, we need 9 subjects to help determine the expert gaze pattern. Again, 60 subjects will be required for 20 in each study arm when examining explicit, implicit, and sham gaze training. Both of these studies lead to our large cross design with four separate study arms. Therefore, a total of 80 subjects will be required for completion of Aim 3. Based on our prior experience with longitudinal designs, we accounted for attrition of about 40 subjects, resulting in a total study sample of 249.

These numbers are sufficient to obtain accurate pilot data in tDCS and gaze training in order to further direct our research going forward. The sample sizes utilized will be larger than most in published surgical education literature, which will emphasize our ability to complete thorough and novel research here at a large undergraduate and medical campus.

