Participants will be recruited mostly via email to the Duke Undergraduate pre-health students and the Duke University School of Medicine general surgery interest group. Attending surgeons will also be invited to participate via email as well as in person through study staff. The Interdisciplinary Behavioral Research Center (IBRC) will also circulate the study to individuals registered in its database, according to IBRC established standards, in order to access a wider array of potential novice participants. Participants will be enrolled once they sign the approved informed consent form, at which point they will complete a questionnaire evaluating inclusion and exclusion criteria and demographics. The Duke University campus includes this large pool of possible subjects which is optimal for recruiting participants with varying exposure to surgical technical skill. Recruitment materials and the information covered by the questionnaire are provided in separate document.

Potential participants will be asked to come to the SEAL simulation lab, located on the 5th floor of the Mary Duke Biddle Trent Semans Center for Health Education. Here, they will be provided a full description of the study, asked to read and sign the consent form, and undergo a qualifying interview. The reviewed information will be obtained from the subject via face-to-face interview and will be restricted to answers to questions intended to determine whether subjects meet entry criteria. All information obtained during this review will be handled confidentially. Subjects will participate voluntarily and will be compensated \$15/hour (3 sessions in Aim 1) and \$10/hour (6 sessions in Aim 2) for their time.

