## **9. Study Interventions**

### **9.1. Fundamentals of Laparoscopic Surgery procedure**

To evaluate expert performance and the effectiveness of each training intervention, this study will utilize a portion of the Fundamental Laparoscopic Skills (FLS) curriculum. FLS is a curriculum that targets basic laparoscopic skills required for success in the variety of operations that are performed with the minimally invasive technique. The FLS curriculum has been validated as translatable to the operating room, and completion is required by The American Board of Surgery to be eligible for certification. FLS consists of five pre-defined skill modules with timed assessments. The current study will utilize only FLS module 1 (module 1 for Aim 1, both modules for Aim 2 and Aim 3) which are performed on the standard laparoscopic box trainer. Based on the average times for completion as well as the average number of repetitions required to achieve proficiency, both of these skills are developed over a prolonged time period making them ideal training models for this study.

FLS module 1 is the Peg Transfer task in which two Maryland dissectors are used to move 6 objects from the subject's left side of the pegboard to the right and back. The transfer between hands must be done in the air without assistance from the pegs. Time penalties are incurred if the object is dropped outside the field of view. Timing stops upon release of the last object.

In the current study pending the Aim, these two modules will be used as both the assessment benchmarks and as the training tasks. As illustrated in **Table 1**, each participant will perform four 20-minute training sessions on the tasks over one to three weeks while

receiving their group-specific augmentation. If the participant is in Experiment 3, an additional follow up session will be scheduled approximately 4-6 weeks after the end of the main training procedure to evaluate retention of learned skills.

Visit 1	Visit 2	Visit 3	Visit 4	Visit 5	Visit 6
90 minutes	60 minutes	60 minutes	60 minutes	60 minutes	60 minutes
Introduction Screening Consent Videos Acclimation Pretest Task A – 20min Break 5 min Task B – 20 min	Acclimation Task A – 20min Break 5 min Task B – 20 min	Acclimation Task A – 20min Break 5 min Task B – 20 min	Acclimation Task A – 20min Break 5 min Task B – 20 min	Acclimation Task A – 20min Break 5 min Task B – 20 min	Acclimation Task A – 20min Break 5 min Task B – 20 min Posttest

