**Table 1:** Experimental protocol and activities. Tasks A and B correspond to the FLS module 1, which will be counterbalanced over participants and sessions pending Aim. All 3-6 visits will occur within 1-3 weeks, again pending Aim. An additional follow up visit (not shown here) will occur at approximately 4-6 weeks for participants in Exp 3.

Prior to the start of FLS activities, each participant will begin by watching two videos demonstrating how to correctly complete FLS modules 1 and 5 (links below). After watching these videos, participants will be instructed by the experimenter on how to use the device and will have the opportunity to practice 2-4 trials to become familiar with the equipment before starting the experiments. In order to carry out quantitative assessment of the training interventions, video will be recorded directly from the box trainer video screen (showing only the tools and the FLS objects). This video will be coded to document the number of repetitions, completion times, and FLS scores for each task.

Data collected from these FLS modules will provide the core dependent variables in our analyses. This will include the number of repetitions and completion times for each of the tasks performed during the sessions. Progress through each of the training sessions and over multiple training sessions will be recorded in the form of behavioral learning curves. Completion times will be based upon official FLS scoring utilizing video coding for most accurate data.

FLS video modules:

<https://www.youtube.com/watch?v=gAQPXHWqdXQ>

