#### 9.5. Combination of tDCS and GT (Experiment 3)

Experiment 3 will include the tDCS and GT approaches described above in a 2 by 2 crossed design with four cohorts: active tDCS and gaze training, active tDCS without gaze training, gaze training with sham tDCS or just sham tDCS. For each of the interventions, the most effective parameter will be chosen (implicit or explicit for gaze training, and bilateral or vertex tDCS), based on the results from the two previous experiments.

This protocol will unfold in the same manner, and under the same schedule as described for Experiments 1 and 2, except that participants will be exposed to different combinations of interventions and will be asked to return for a 4-6 week follow up visit in which they only perform the FLS modules without intervention (no tDCS or GT).

In regard to the interventions outlined here, [name], the General Surgery Research Fellow in charge of all enrollment and participation, has all necessary training for tDCS and eye tracker technology to ensure these are used safely and administered according to proper procedures.

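### Experiment 3 tests retention 4-6 weeks after training, but the plan neither restricts nor records outside practice in that gap, so the contrast may be noisier, diluted or biased in either direction as a measure of retention

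*Combined protocol and SAP*

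**What the plan says.** Section 4 (Experiment 3) plans a "follow-up FLS assessment 4 to 6 weeks after the completion of training to evaluate the retention of trained skills". It attaches a directional hypothesis: the combination "will lead to greater retention of trained skills at the follow up assessment, compared to either condition alone or to the sham group". Section 2 also names retention as part of the study's purpose.

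The visit is described twice more. Section 9.1 says that "an additional follow up session will be scheduled approximately 4-6 weeks after the end of the main training procedure". Section 9.5 says that participants "will be asked to return for a 4-6 week follow up visit in which they only perform the FLS modules without intervention". That last condition governs what happens at the visit, not in the weeks before it.

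On data, section 9.1 states: "This will include the number of repetitions and completion times for each of the tasks performed during the sessions". Surgical exposure is asked about at the screening interview (section 7), and no repeat at follow-up is described. Section 12 gives testing schedule, age and gender as examples of moderators.

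On practice effects, section 6 explains that each aim needs new subjects "due to the improvement in technical skill from repetition alone". Recruitment is mainly by email to undergraduate pre-health students and the medical school's "general surgery interest group", with a behavioural research database as a further source of novices.

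**The concern.** The plan treats repetition as powerful enough that nobody may serve in two experiments. By the same reasoning, repetition outside the study between the last training session and the retention test can change the follow-up score. The gap of 4-6 weeks is longer than the 1-3 weeks of training. Some participants have a career interest in laparoscopic skills, and section 10.4 presents FLS repetitions as a benefit to them.

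Randomisation balances the inclination to practise at entry. It does not balance practice that follows from the assigned arm. For example, people who finished training more slowly might practise more to catch up. Participants who reviewed an expert's gaze or trained under a mask (section 9.4) also know what they did.

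At stake is how the retention result is interpreted. Without a record of practice, a difference at follow-up, or its absence, cannot be separated into skill kept and skill newly gained. That information cannot be reliably recovered at the analysis stage.

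**Working it through.** **The plan's own figures.** Section 6 gives 3×20 + 9 + 3×20 + 4×20 = 209 completers, and 209 + 40 = 249 enrolled. Both reproduce, and this point changes neither. The plan states no effect size, SD, significance level or power, so there is no power figure to reproduce.

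**Inputs.** From section 4: four groups of 20, hence 20 v 20 for the combined arm against any other arm, and 40 v 40 for each main effect of the 2 by 2 design. Assumed for illustration: two-sided 5% test, SD = 1, true standardised difference d = 0.8, and a share p = 10%, 20% or 30% practising in the gap.

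**Formula.** Normal approximation: power = Φ( d / (SD × √(2/n)) − 1.96 ).

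With no practice and n = 20: 0.8/√0.1 = 2.530, and Φ(0.570) = 71.6%. With n = 40: 0.8/√0.05 = 3.578, and Φ(1.618) = 94.7%.

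**Case (a): practice erases the arm difference in those who practise, at the same rate in each arm.** The observed difference is 0.8(1 − p), that is 0.72, 0.64 or 0.56.

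**Case (b): practice adds the same 1 SD gain at the same rate in each arm.** The mean difference stays at 0.8, and the SD becomes √(1 + p(1 − p)), that is √1.09, √1.16 or √1.21.

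| Share practising | (a) 20 v 20 | (a) 40 v 40 | (b) 20 v 20 | (b) 40 v 40 |
|---|---|---|---|---|
| 0% | 71.6% | 94.7% | 71.6% | 94.7% |
| 10% | 62.4% | 89.6% | 67.8% | 92.9% |
| 20% | 52.5% | 81.7% | 65.1% | 91.3% |
| 30% | 42.5% | 70.7% | 63.3% | 90.2% |

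**Case (c): practice differs by arm.** With 30% practising in one arm, 10% in the other and a 1 SD gain, the shift is (0.30 − 0.10) × 1 = 0.2 SD. A true 0.8 is seen as 1.0 or 0.6, depending on which arm practises more. A true zero is seen as +0.2 or −0.2.

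The direction and size of the effect therefore depend on how practice acts and who does it. The plan collects neither piece of information.

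**The case against.** A reader might infer that the retention test does mix retention with fresh training and so dilutes the arm difference. The documents do not support that. No section shows that anyone practises in the gap or has a box trainer outside the study; the only facility described is the study's own simulation laboratory. Dilution is also just one outcome: case (b) leaves the mean difference intact, and case (c) can enlarge it. Quoting only the equivalent sample inflation for case (a), 1/(1 − p)² = 1.23, 1.56 or 2.04, would present the erasing case as if it were the whole range.

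A reader might also infer that the follow-up result becomes uninterpretable. It does not. All randomised participants can still be compared on skill at 4-6 weeks. Only the attribution of that contrast to retention is qualified.

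Other points on the plan's side have some force. Recruitment through the research database widens the pool beyond people with surgical ambitions. Residents and attendings appear to serve the nine-person expert sample, since section 9.4 limits gaze training to novices. The Experiment 3 consent form is still to be written, and is intended to keep subjects blinded (section 7). The screening questionnaire is a separate document. Either could carry an instruction that is not visible here. The moderator list in section 12 is open-ended, and the plan describes its numbers as adequate for pilot data.

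These points limit how strongly the concern can be put, but they do not remove the omission. An open moderator list cannot use practice that was never recorded, and a blinded consent does not by itself control what people do after training.

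**Conclusion.** The point holds as a cheap improvement of low severity. In the visible text, practice between training and the retention test is neither restricted nor recorded, although the plan's own reasoning treats repetition as a cause of improvement and retention carries its own hypothesis. If participants practise, the contrast may be noisier, diluted or biased in either direction as a measure of retention.

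The size rests entirely on assumptions: d = 0.8, SD = 1, a two-sided 5% test, 10-30% practising and, where relevant, a 1 SD gain. On those, the loss of 20 v 20 power runs from about 4 percentage points (71.6% to 67.8%) to about 29 (71.6% to 42.5%), and a 30% v 10% imbalance moves the estimate by 0.2 SD. If nobody practises, there is no effect.

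**What to change.** In section 9.5, and in the Experiment 3 consent form still to be written, ask participants not to practise these tasks on box trainers, simulators or FLS equipment outside study sessions until the follow-up visit. At that visit, record the hours and type of any such practice.

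In section 12, keep the comparison of all randomised participants as the main retention analysis and report practice by arm beside it. Any analysis that leaves out those who practised should be labelled exploratory. Practice happens after randomisation and may depend on arm or on learning speed, so excluding on it can remove slow learners unequally and create bias of its own.

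The cost is one instruction, one question at a visit already planned, and a short addition to the analysis section. The downsides are reliance on self-report and a short limit on outside practice for people who may want it. The instruction and question need to be in place before Experiment 3 begins.

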## **5. Selection of Subjects**

Inclusion/Exclusion criteria were chosen to allow us to meet our study aims while following safety protocols that have been well-defined in prior studies.

### tDCS portion

#### Inclusion Criteria:

- 1) Age  $\geq 18$  years, healthy male and female
- 2) Negative urine pregnancy test for female participants
- 3) Willing and able to provide informed consent
- 4) Able to follow study procedures

#### Exclusion Criteria:

- 1) Indwelling metallic implants
- 2) Neurological or psychiatric medical history
- 3) Drug or alcohol abuse
- 4) Current or prior brain tumor
- 5) Current or prior seizures
- 6) Neuroactive medications
- 7) Current pregnancy
- 8) Damage, rash, or skin lesion in area of electrode placement
- 9) Blindness
- 10) Inability to read and/or understand English

### Gaze training portion

#### Inclusion Criteria:

- 1) Age  $\geq 18$  years, healthy male and female
- 2) Willing and able to provide informed consent
- 3) Able to follow study procedures

#### Exclusion Criteria:

- 1) Blindness
- 2) Inability to read and/or understand English

